7.5 Interim Reporting

7.5.1 Monthly Reports to Sites

Reports of accrual information, outstanding queries, and protocol violations will be distributed to the sites monthly.

7.5.2 Quarterly DSMB Reports

The DSMB will receive quarterly updates on:

- Site status;
- Accrual overall and by site;
- Study compliance issues; and
- The status of adverse event monitoring:
 - When the monthly summaries of Grade 3+ transfusion related events were prepared and discussed;
 - Whether the continuous review or monthly discussion raised issues which were reported to NHLBI as being of possible concern; and
 - Any actions taken in response to those concerns.

7.5.3 Semi-Annual DSMB Reports

The DSMB will meet every 6 months, either in-person or via teleconference. Reports will include:

- Baseline characteristics overall and by treatment arm;
- Formal interim looks at:
 - Primary study endpoint,
 - Highest grade of bleeding,
 - Death due to bleeding,
 - All cause mortality,
 - Bleeding severity (if validated scale available);
- Serious adverse events overall and by treatment arm;
- Transfusion-related events of all severity levels overall and by treatment arm;
- Site status;
- Accrual overall and by site; and
- Study compliance issues.

8. STATISTICAL CONSIDERATIONS

8.1 Analysis Plan

The primary analysis for the primary endpoint, the percentage of patients with at least one episode of Grade 2 or higher bleeding, will be three one-degree-of-freedom chi-square tests, each comparing a pair of treatment groups. These tests will be carried out at the .017 significance level to adjust for the multiple comparisons.

These analyses will be done on an intention-to-treat basis. That is, patients will be counted in the treatment arm to which they were randomly assigned, even if they actually received transfusions that were not according to their assigned dosing strategy. Any such "crossovers" between treatment arms will tend to make the observed percentages of patients with Grade 2 or higher bleeding more similar between treatment arms than they would have been if all patients had been treated according to their assigned dosing strategy. Thus, an intention-to-treat analysis is conservative.

The most important secondary endpoints, capturing key data on costs and safety, are the total number of platelets dispensed, the total number of transfusion events, the highest grade of bleeding, and the bleeding severity score (if such a score has been validated and published by the end of the Platelet Dose trial, and the necessary information to calculate the score was collected). These endpoints capture the main components of transfusion costs and seriousness of bleeding. Differences between each pair of treatment arms for these three or four pre-specified key secondary outcomes will be tested, each at the .017 significance level, also on an intention-to-treat basis. For other secondary outcomes, only descriptive data will be presented.

Platelet usage, number of transfusion events, and the severity score (if continuous) are expected to have highly skewed distributions, so for these endpoints a log transform (or other suitable transform) will be carried out before using a t-test to compare treatment arms. If no acceptable transform can be found, a Wilcoxon rank sum test will be used instead of the t-test.

In the analysis of highest grade of bleeding, some grades are expected to be quite rare. Proc StatXact will be used for each of the 2x4 tables to obtain precise Monte-Carlo estimates of the p-value for an exact Kruskall-Wallis test for treatment differences, where the bleeding grades are considered ordered. If the severity score is ordinal, similar analyses will be carried out for that outcome.

Per-protocol and covariate-adjusted analyses will also be performed as secondary analyses.

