4.2 Stratification and Randomization

Treatment groups will be allocated using randomly permuted blocks within strata (Zelen, 1974). Four strata will be used: chemotherapy for hematologic malignancy, chemotherapy for solid tumors, stem cell transplant (allogeneic) and stem cell transplant (autologous or syngeneic). Treatment allocation will also be balanced within each clinical center using dynamic balancing (Zelen, 1974).

Patients will be randomized with equal allocation to three platelet transfusion therapy groups based on body surface area (BSA):

Lower dose: $1.1 \ge 10^{11}/\text{m}^2$ (½ of the medium dose) Medium dose: $2.2 \ge 10^{11}/\text{m}^2$ Higher dose: $4.4 \ge 10^{11}/\text{m}^2$ (twice the medium dose)

An acceptable dose will be a dose that is within a range of 25% either above or below the target dose.

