8.2 Sample Size and Power

The primary endpoint for the study is the percentage of patients with at least one episode of bleeding at Grade 2 or higher, as determined by the Platelet Dose Trial Bleeding Scale.

Eighty-five percent power was desired to detect an absolute difference of 12.5% between any pair of dose strategies. The estimated percentage of patients who will experience Grade 2 or higher bleeding is 50%. Sample size for a chi-square test at the .017 level was calculated for a scenario with true percentages of 43.75% and 56.25%, assuming an interim monitoring plan with three interim looks and one final look. (See section 7.2.) Without taking into account loss to follow-up, 389 patients per arm (1167 patients in all) would be needed to achieve 85% power. This sample size would also provide 80% power to detect a treatment arm difference if the true percentages were 44.1% and 55.9% (an absolute difference of 11.8%) and 90% power to detect a treatment arm difference if the true percentages were 43.3% and 56.7% (an absolute difference of 13.4%). A sample size of 445 per arm would be needed for 90% power to detect a difference with true percentages of 43.75% and 56.25%.

Because the patients in this study will be hospitalized, loss to follow-up is expected to be no more than 10%. Conservatively allowing for 13.5% loss to follow-up, the target sample size is 450 patients per arm (1350 patients in all).

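### Randomisation is stratified by four disease/treatment groups, but the primary and interim tests ignore the strata: valid and adequately powered, yet forgoing efficiency if the strata predict bleeding

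*Protocol*

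**What the plan says.** Protocol section 4.2: "Treatment groups will be allocated using randomly permuted blocks within strata". The four strata are chemotherapy for haematologic malignancy, chemotherapy for solid tumours, allogeneic transplant, and autologous or syngeneic transplant. Centre is handled separately: "Treatment allocation will also be balanced within each clinical center using dynamic balancing". Allocation across the three arms is equal.

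Protocol section 8.1: the primary analysis "will be three one-degree-of-freedom chi-square tests, each comparing a pair of treatment groups", and "These tests will be carried out at the .017 significance level to adjust for the multiple comparisons". Section 7.4.1 and its Table 5 apply one-degree-of-freedom chi-square tests at all four looks. Neither section mentions the strata. The only place for adjustment is a closing sentence of 8.1: "Per-protocol and covariate-adjusted analyses will also be performed as secondary analyses".

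Protocol section 8.2: "Eighty-five percent power was desired to detect an absolute difference of 12.5% between any pair of dose strategies". The calculation is for a chi-square test at 0.017 with rates of 43.75% and 56.25%, and it uses one overall bleeding rate of 50%. It takes no credit for stratification. No section gives stratum shares or stratum-specific bleeding rates.

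**The concern.** Blocking within strata makes the arms nearly equal in stratum mix, so differences in bleeding between strata largely drop out of the comparison of arms. The ordinary chi-square does not know this. Its variance uses the overall rate, p(1 − p), which still contains the between-stratum part. If the strata differ in bleeding risk, the standard error is larger than the real sampling variation of the difference. The test then rejects less often than its nominal level allows, and detects a true difference less often than a stratified test on the same patients would.

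The synopsis presents the trial as a study of the safety of three dosing strategies. A conservative test is not automatically the cautious choice there, because a non-significant result may be read as support for using fewer platelets. The same conservatism applies at the interim looks, where the monitoring board is looking for harm.

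**Working it through.** **1. The plan's own figures.** Inputs from sections 7.4.1 and 8.2: 43.75% v 56.25%, level 0.017 (taken as two-sided, as a chi-square test implies), power 85%, four equally spaced looks, 13.5% loss.

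- Fixed design: n = [2.387·√0.5 + 1.036·√0.4922]² / 0.125² = 373.2, so 374 per arm. With continuity correction it is 390 after rounding up.
- Group-sequential design without continuity correction: inflation 1.010, about 378 per arm.
- The stated 389 lies within 3% of both. 389 / (1 − 0.135) = 450, as stated.
- Lan-DeMets O'Brien-Fleming type spending of 0.017 over four looks gives <0.0001, 0.0004, 0.0046 and 0.0155, as in Table 5.
- Group-sequential power of the planned test at 389 per arm with no stratum differences: 86.1%. The promised 85% is met.

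**2. Effect of ignoring prognostic strata.** Let R² be the between-stratum variance of bleeding divided by 0.25, the total variance at an overall rate of 50%. If strata are balanced across arms, the unstratified statistic has null standard deviation √(1 − R²) instead of 1. At a single look its true level is 2·[1 − Φ(2.387/√(1 − R²))].

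Worked case, with assumed shares of 30/5/40/25% in the order in which the strata are listed above and assumed rates of 49.3/19.3/67.3/29.3%:

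- R² = [0.30·0.007² + 0.05·0.307² + 0.40·0.173² + 0.25·0.207²] / 0.25 = 0.110.
- 2.387/√0.890 = 2.529, so the single-look level is 0.0114. Carried through the four boundaries it is 0.0112.

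**3. Range.** All stratum shares and rates are assumed: shares as above, except equal shares in the last row. There are 389 per arm and four looks, with a common odds ratio chosen to give a 12.5-point overall difference.

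| Stratum rates | R² | True level, unstratified | Power, unstratified | Power, stratified |
|---|---|---|---|---|
| all 50% | 0 | 0.0170 | 86.1% | 86.1% |
| about 42-54% | 0.005 | 0.0167 | 86.3% | 86.4% |
| about 30-60% | 0.034 | 0.0151 | 86.5% | 87.5% |
| about 19-67% | 0.11 | 0.0112 | 87.4% | 90.3% |
| 20-80% | 0.20 | 0.0073 | 88.6% | 93.2% |

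Put another way, a stratified test would reach roughly the 86% of the first row with about 387, 376, 348 and 314 per arm in rows two to five.

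**4. Simulation checks.** A single-look simulation of 200,000 trials per row of the table, at nominal 0.017, agrees. In the 19-67% case the unstratified test rejects 1.1% of null trials and the stratified test 1.7%, with power 87.6% v 90.6%. Across all rows the stratified test's null rejection rate lies between 1.6% and 1.8%. Separate single-look simulations at the final threshold of 0.0155 give a gain of about 0.5 points for rates of 30-60%, 2.3 to 2.4 points for 25-70% (level 0.011), and 3.6 to 3.9 points for 20-75% (level about 0.008).

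**5. Interim looks.** At R² = 0.11, √(1 − R²) = 0.944. The second and third boundaries, z = 3.543 and 2.833, become 3.755 and 3.002 on the true scale. Table 5's 0.0004 and 0.0046 then act like about 0.0002 and 0.0027.

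**The case against.** The strongest reply is that nothing is broken. Sections 7.4.1, 8.1 and 8.2 name the same test at the same level, and the sample size matches it. Section 7.4.1 promises an error of no more than 0.017 per pair, and a conservative test honours that. All of this stands. A reader might infer that the plan loses power it has already paid for. The documents do not support that: the size was set for this chi-square with no credit for stratification, and prognostic strata raise its power slightly, from 86.1% to 88.6% across the table. What is forgone is an unclaimed gain.

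It is also fair that no section says the strata predict bleeding, that gains above 2 points need stratum rates spread over roughly 45 points or more, and that centre balancing means the protocol does not guarantee exact balance within strata. These limit the size of the point, not its direction. Section 8.1 does plan covariate-adjusted analyses, and leaving the covariates to a statistical analysis plan is normal. But 8.1 itself fixes the primary test and places adjustment outside it.

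Finally, if the analysis should follow the randomisation, centre could be argued for too. The point here is confined to the four strata used for blocking. The number of centres is not given, and many small centres would make thin tables.

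**Conclusion.** The point holds as one of efficiency and of consistency between randomisation and analysis. It is not a fault of validity or sizing. The primary and interim tests leave out the randomisation strata. If those strata predict bleeding, the true per-pair level falls below 0.017 and the trial forgoes power: about 0 to 1 point when differences are weak to moderate, about 2 to 5 points when they are strong to extreme, with the level then near 0.011 and 0.007-0.008 respectively. If stratum rates are equal, the two tests perform alike. These figures assume stratum shares and rates that the protocol does not give, an overall rate of 50%, a common odds ratio and close balance within strata. The true gain cannot be fixed from the document.

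**What to change.** In sections 7.4.1 and 8.1, make each pairwise primary test the one-degree-of-freedom Cochran-Mantel-Haenszel test stratified by the four randomisation strata. Report with it a stratum-weighted risk difference and its confidence interval. Keep the Table 5 boundaries and the sample size as they are; the statistic still has one degree of freedom. Report the unstratified chi-square as a sensitivity analysis.

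The cost is about one sentence in each section. The strata are known at randomisation, so no further data or patients are needed. The change should be made before any comparison by arm is seen.

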7.4.1 Interim Analyses of Primary Endpoint

Sample size calculations have been based on the assumptions that

- There will be four equally spaced looks planned for the primary endpoint, i.e. interim looks after outcome data have been obtained for approximately 112, 225, and 337 patients per arm, and a final look at the end of the study;
- The primary endpoint will be analyzed at each look using separate pairwise comparisons between each pair of treatment arms still enrolling patients at that look; and,
- A Lan-DeMets alpha spending function similar to O'Brien-Fleming boundaries will be used for each pair of treatments, with a nominal p-value of .017 for each pair (i.e. using Bonferroni adjustment for the three pairwise comparisons).

This approach controls the Type I error for each pair of treatments to be no more than 0.017 even if a decision is made to discontinue one treatment arm partway through the study.

This approach means that an extremely large difference between two treatment arms in the percentage of patients with Grade 2 or higher bleeding would be needed to cross a stopping boundary at the first look. The boundary becomes less stringent at later looks. If the study continues to its planned number of patients, the treatment difference needed to declare statistical significance will be only slightly larger than the critical value that would be used if there were no interim looks. Table 5 shows the p-values that would be needed for each one-degree-of-freedom chi-square test at each look to declare that the boundary had been crossed. At an interim look, this would suggest that stopping the trial, or one arm of the trial, should be considered. If the study continues to the planned number of patients, crossing the boundary would be

considered necessary to declare a statistically significant difference between the two arms with an alpha level of 0.017.

Look	p-value
1 st interim look	< 0.0001
2 nd interim look	0.0004
3 rd interim look	0.0046
Final look	0.0155

Table 5: P-value boundaries using Lan-DeMets O'Brien-Fleming type boundaries

If the DSMB meetings do not take place at exactly the planned number of subjects, the EAST-3 software package can be used to adjust the critical p-value at each look to ensure that the overall significance level of 0.017 for each pairwise comparison of the primary endpoint is maintained.

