7.4.2 Interim analyses of safety-related secondary endpoints

Several of the secondary endpoints listed in Section 2.2 are related to patient safety. These include secondary endpoints 13 (highest grade of bleeding while on study), 14 (if a validated published severity scale which we can calculate from study data becomes available), 15a (death due to bleeding), and 17 (all-cause mortality).

At each scheduled DSMB meeting data will be presented regarding the proportion of patients in each treatment arm with death due to bleeding and with death from any cause. P-values for chi-square tests (or, for rare outcomes, Fisher's exact tests) comparing each pair of treatment arms will be provided. Data will also be presented regarding the proportion of patients in each treatment arm who reach each grade of bleeding, and Cochran-Mantel-Haenszel tests of trend (or similar exact tests, for rare outcomes) will be presented for each pair of treatment groups. If an ordinal severity scale is available, a similar approach will be taken. If an essentially continuous severity scale is available, it will probably be highly skewed. The mean, standard deviation, and quartiles of the score will be presented for each group. If a log transform or other suitable transform can be found, the data will be transformed before using t-tests to compare each pair of treatment arms. Otherwise, Wilcoxon rank sum tests will be used to compare each pair of treatment groups. For each of these secondary outcomes, the p-value boundaries in Table 5 will be used when considering whether to stop the trial or one arm of the trial.

Early stopping guidelines based on endpoints related to blood component usage or transfusion events are not proposed, because these endpoints are related to the economics of health care rather than patient safety.

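### Section 8.1 gives .017 as the final test level without reference to the 0.0155 final-look boundary, and the interim-monitored key secondary endpoints have no other final level

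*Protocol*

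**What the plan says.** **Primary endpoint, final analysis (Protocol 8.1).** The primary analysis is "three one-degree-of-freedom chi-square tests, each comparing a pair of treatment groups". On the level: "These tests will be carried out at the .017 significance level to adjust for the multiple comparisons". Multiple comparisons are the only reason given. Interim looks, Table 5 and 0.0155 are not mentioned.

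**Primary endpoint, monitoring (Protocol 7.4.1).** "There will be four equally spaced looks planned for the primary endpoint". A Lan-DeMets spending function of O'Brien-Fleming type is used for each pair, "with a nominal p-value of .017 for each pair (i.e. using Bonferroni adjustment for the three pairwise comparisons"). Table 5 lists the p-values needed: below 0.0001, 0.0004, 0.0046 and, at the final look, 0.0155. The section says that, at the planned end, the boundary must be crossed before a difference is called significant at alpha 0.017. It also says: "This approach controls the Type I error for each pair of treatments to be no more than 0.017".

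**Monitored secondary endpoints (Protocol 7.4.2 and 7.5.3).** Highest grade of bleeding, the severity score if available, death due to bleeding and all-cause mortality have formal interim looks. "For each of these secondary outcomes, the p-value boundaries in Table 5 will be used when considering whether to stop the trial". The same applies to stopping a single arm. No level for the final test is given in these sections.

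**Key secondary endpoints, final analysis (Protocol 8.1).** Pairwise differences for the "three or four pre-specified key secondary outcomes will be tested, each at the .017 significance level, also on an intention-to-treat basis". These are platelets dispensed, transfusion events, highest grade of bleeding and, if available, the severity score. The monitored and unmonitored endpoints are not distinguished.

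**The concern.** In a group-sequential design the overall level and the p-value needed at the last look are different numbers, because part of the alpha has been spent earlier. Section 8.1 is where an analyst will look for the final threshold. It gives the overall level with no sign that it is not the cut-off to apply.

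For the primary endpoint, someone programming from 8.1 alone would compare each p-value with .017, while 7.4.1 requires 0.0155. A final p-value between the two would raise a question best settled before the data are seen.

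For highest grade of bleeding and the severity score the gap is more substantive. They are examined repeatedly against Table 5, but nothing in the protocol tells the analyst to use anything stricter than .017 at the end.

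**Working it through.** **Inputs.** Two-sided one-degree-of-freedom tests (8.1); four equally spaced looks, so information fractions t = 0.25, 0.50, 0.75 and 1.00 (7.4.1); overall alpha 0.017 per pair (7.4.1); final-look boundary 0.0155 (Table 5); level in 8.1, .017.

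**Step 1: reproduce Table 5.** Apply O'Brien-Fleming-type spending to each side at 0.0085. The cumulative two-sided alpha spent by time t is

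4 × [1 − Φ(z / √t)], where z = 2.6315 is the upper 0.00425 point of the normal distribution.

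Solving for the boundaries by recursive numerical integration of the joint distribution of the test statistics gives:

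| Look | t | Cumulative alpha | Boundary z | Two-sided p | Table 5 |
|---|---|---|---|---|---|
| 1 | 0.25 | 0.0000003 | 5.134 | 0.0000003 | < 0.0001 |
| 2 | 0.50 | 0.00040 | 3.543 | 0.0004 | 0.0004 |
| 3 | 0.75 | 0.00475 | 2.832 | 0.0046 | 0.0046 |
| 4 | 1.00 | 0.01700 | 2.4205 | 0.0155 | 0.0155 |

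Table 5 is correct. With 0.0155 at the final look the per-pair error is 0.0170, as 7.4.1 states.

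**Step 2: replace the final boundary with a nominal .017.** The last critical value falls from z = 2.4205 to z = 2.387. The first three boundaries still spend 0.00475. The probability of first crossing at the last look rises from 0.0170 − 0.00475 = 0.01225 to about 0.01365. The total is 0.00475 + 0.01365 = 0.0184.

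- Absolute excess: 0.0184 − 0.0170 = 0.0014.
- Relative excess: 0.0014 / 0.0170 = about 8%.
- Allowing for rounding in Table 5, and for any first-look boundary up to 0.0001, the total stays between 0.0184 and 0.0185.

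**Step 3: familywise error over the three pairs.** Simulated null trials with three arms of equal size and the same four looks, counting a rejection in any pair, give about 0.045 with a final 0.0155 and about 0.048 with a final .017. Both are below 0.05.

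**Step 4: the monitored secondary endpoints.** A single final test at .017 already uses the whole .017, apart from any slight conservatism of an exact test. If an interim crossing of Table 5 also counts as a rejection, the total must exceed .017 whatever the number of looks. With the four equally spaced looks of the primary endpoint the figure is that of step 2, about 0.0184. This is an approximation carried over from the primary. No calculation specific to an ordinal grade was made.

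**The case against.** **The primary endpoint is already settled.** A reader might infer that the protocol sets two contradictory thresholds for the primary endpoint, or that it breaks its own per-pair guarantee. The text does not support that. Section 7.4.1 calls 0.017 the overall significance level per comparison and makes crossing the boundary necessary at the planned end. Section 8.2 uses the same shorthand: it calculates the sample size for a test at the .017 level while assuming three interim looks and a final one. Read that way, 8.1 states the Bonferroni share per pair, not a nominal cut-off, and a final p of 0.016 fails the only rule written specifically for the final look. This part of the objection stands. The error of 0.0184 arises for the primary only if 8.1 is applied literally and in isolation.

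**No guarantee covers the secondaries.** The sentence "This approach controls the Type I error for each pair of treatments to be no more than 0.017" stands in the primary-endpoint section. It would be wrong to say that it is breached for highest grade of bleeding. This also stands. The defect there is a final level that is not adjusted for the looks.

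**Interim crossings may not be rejections.** Section 7.4 describes the boundaries as guidelines, and 7.4.2 applies them to decisions about stopping. If a crossing is never treated as a finding of significance on that endpoint, a final test at .017 has error of at most .017. Moreover, the secondaries are reviewed at each scheduled semi-annual DSMB meeting, which need not give four equally spaced looks, and the interim trend test differs from the final exact test. These points make 0.0184 conditional. They do not supply the missing rule: the protocol does not say what an interim crossing means for the final inference on these endpoints.

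**The effect is small.** It is, and familywise error for the primary stays below 0.05 even on the literal reading.

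**Conclusion.** The point holds in a limited form. No figure in Table 5 is wrong.

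- **Primary endpoint:** 8.1 is unclear because it omits the cross-reference to the final-look boundary. Taken literally it would raise the per-pair error from 0.0170 to about 0.0184, and the three-pair familywise error from about 0.045 to about 0.048. Read together with 7.4.1 and 8.2, it does neither.
- **Highest grade of bleeding, and the severity score if available:** the only final level stated is the full .017, although both are monitored against Table 5. The per-pair error would exceed .017. The figure of about 0.0184 rests on four equally spaced looks and on counting an interim crossing as a rejection.
- **Platelets dispensed and transfusion events:** .017 is appropriate as it stands, because section 7.4.2 proposes no early stopping on such endpoints.

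The effect is small. The correction is still worth making, because a decision threshold should be unambiguous before unblinding and the remedy is specific.

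**What to change.** In section 8.1:

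1. State that .017 is the overall level for each pairwise comparison, and that the final primary tests use the final-look boundary of Table 5 (0.0155, or the value recalculated for the looks actually held).
2. Apply the same final boundary to highest grade of bleeding and to any severity score that is monitored.
3. Keep .017 for platelets dispensed and transfusion events.

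This takes two or three sentences. The sample size need not change, since section 8.2 already assumes three interim looks and a final one. For the primary endpoint it only makes explicit what 7.4.1 requires. The cost is a slightly stricter final threshold, 0.0155 instead of .017, for the monitored secondaries.

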2.2 Secondary

To compare the three study arms with respect to the following outcomes:

Platelet Related:

- 1. Platelet utilization rates (total number of platelets transfused x 10^{11}).
- 2. Number of platelet transfusion events; i.e., frequency of transfusions. A transfusion event would be each separate platelet transfusion issued by the trial site's transfusion service.
- 3. Days of platelet support; the number of days from the first to the last platelet transfusion.
- 4. Frequency of platelet transfusions/day of platelet support.
- 5. Total number of platelets transfused $(x10^{11})/day$ of platelet support.
- 6. Total number of platelets transfused $(x10^{11})$ /Body Surface Area (BSA).
- 7. Total number of platelets transfused $(x10^{11})/BSA/day$ of platelet support.
- 8. Number of days with a morning platelet count of $\leq 10,000/\mu$ l.
- 9. Platelet response corrected platelet count increment at ≤ 4 hours post-transfusion.

Corrected count increment = $\frac{\text{(Platelet Increment/µl) x body surface area (m²)}}{\text{(number of platelets transfused) x 10⁻¹¹}}$

- 10. Platelet response corrected platelet count increment based on the platelet count the morning following a platelet transfusion.
- 11. Incidence of platelet refractoriness (defined as two sequential transfusions, each with CCIs < 5,000 measured within 4 hours post-transfusion).

Hemostasis Related:

- 12. Number of days to first Grade 2+ bleeding.
- 13. Highest category of bleeding during time on study (Platelet Dose Trial Bleeding Scale Grades ≤1, 2, 3, 4 by arm).
- 14. Bleeding severity based on number of days with bleeding (total days of bleeding and bleeding/thrombocytopenic day), intensity of bleeding, and number of sites with bleeding, if such a severity score has been validated and published by the time this trial is completed.

- 15. Surrogate outcomes for hemostatic efficacy to include:
 - a) Death due to bleeding as the primary or contributory cause of mortality.
 - b) Number of platelet transfusions given above the 10,000/ μ l platelet transfusion trigger, number of platelet transfusions given more often than once/day, and/or number of platelet transfusions given above their assigned dose, in each case because of \geq Grade 2 bleeding (as determined by the Platelet Dose Trial Bleeding Scale).
 - c) Number of platelets (x 10^{11}), frequency of transfusions and duration of transfusions given because of \geq Grade 2 bleeding (as indicated in 15b).

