3. STUDY POPULATION

3.1 Inclusion Criteria

- 1. Patients with, or expected to have, hypoproliferative thrombocytopenia who are expected to have a platelet count of $\leq 10,000 \mu l$ for ≥ 5 days, and be in the hospital for ≥ 5 days.
- 2. Weight between 10 and 135 kilograms.
- 3. Patients whose PT/INR, PTT and fibrinogen assays, measured within 72 hours before study entry, are as follows:
 - a) $PT \le 1.3 X$ upper limit of normal for the laboratory
 - b) PTT \leq 1.3 X upper limit of normal for the laboratory
 - c) Fibrinogen $\geq 100 \text{mg/dL}$
- 4. Patients with any diagnosis undergoing or with completed hematopoietic stem cell transplantation, and patients with a diagnosis of acute or chronic leukemia, non-Hodgkins and Hodgkins lymphoma, myeloma, myelodysplasia, or non-hematologic malignancy undergoing or with completed chemotherapy.
- 5. During this hospitalization, the patient has not yet received any platelet transfusions related to the current or planned course of therapy. Individual platelet transfusions given prior to the study and unrelated to thrombocytopenia will not exclude the patient.

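### The key secondary test of total platelets leaves out body surface area, which sets every assigned dose; adding it as a covariate would recover a modest amount of precision

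*Protocol*

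**What the plan says.** Protocol section 8.1 states that the most important secondary endpoints "are the total number of platelets dispensed, the total number of transfusion events, the highest grade of bleeding", and a bleeding severity score if one is available. It gives the reason for the choice: "These endpoints capture the main components of transfusion costs and seriousness of bleeding". Differences between each pair of arms on these "key secondary outcomes will be tested, each at the .017 significance level, also on an intention-to-treat basis".

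On method, section 8.1 says "Platelet usage, number of transfusion events, and the severity score (if continuous) are expected to have highly skewed distributions", and therefore "a log transform (or other suitable transform) will be carried out before using a t-test to compare treatment arms". A Wilcoxon rank sum test is the fallback if no transform is acceptable. No covariate enters either test. Section 8.1 closes by placing covariate-adjusted analyses among the secondary analyses, without naming covariates.

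Platelets per BSA, and per BSA per day of support, are secondary outcomes 6 and 7 in section 2.2. They are outside the key set, and section 8.1 says of such outcomes: "For other secondary outcomes, only descriptive data will be presented".

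Dose is assigned per square metre in all three arms (section 4.2). Eligibility is "Weight between 10 and 135 kilograms" (section 3.1), and section 6.2 provides for pediatric specimens, so children are expected. Height and weight are entered at enrolment (section 4.3). Randomisation uses four treatment strata with balancing by center (section 4.2); body size is not a factor.

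**The concern.** A transfusion given at the assigned dose is a fixed multiple of the patient's BSA. Two patients in the same arm with the same number of such transfusions can therefore differ several-fold in total platelets for no reason other than size. The planned test treats that difference as noise, although its source is measured before randomisation and is the quantity the protocol uses to set the dose.

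At stake is the power of the pairwise comparisons on the main resource-use endpoint. This matters most if the true difference in use between adjacent dose arms is small, since a missed difference there would weaken the economic conclusion of the trial.

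**Working it through.** **The plan's own figures.** The protocol gives no SD, effect size or power for total platelets, so there is no stated figure for this endpoint to reproduce. Its sample size is for the primary endpoint and does reproduce: 43.75% against 56.25% at alpha 0.017 and 85% power gives 390 per arm with continuity correction (protocol: 389), and 389/(1 − 0.135) = 449.7, i.e. 450.

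**Inputs from the protocol.** Alpha 0.017 per pair (section 8.1, taken as two-sided, z = 2.387); 450 per arm (section 8.2); 15% more platelet use at the highest dose of one dose study, and 22% less use with pools of 3 rather than 6 concentrates in a model (both section 1).

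**Assumptions.**
- SD of log total platelets (s): 0.6 to 1.0.
- SD of log BSA (b): 0.13 for adults only, to 0.29 with 15% children.
- Log total platelets equals log BSA plus an independent remainder, so adjustment reduces the SD from s to √(s² − b²).

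**Range of BSA.** By the Mosteller formula with assumed heights of 75 and 185 cm: √(10×75/3600) = 0.46 m² and √(135×185/3600) = 2.63 m², nearly a six-fold range.

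**Formula.** Power = Φ( ln(ratio) / (SD × √(2/450)) − 2.387 ), with √(2/450) = 0.0667.

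**Central case, s = 0.8, b = 0.25.** Share of variance removed: 0.25²/0.8² = 0.098. Adjusted SD: √(0.64 − 0.0625) = 0.760.
- 15% more use, ln 1.15 = 0.1398. Unadjusted: 0.1398/(0.8 × 0.0667) − 2.387 = 0.234, power 59.2%. Adjusted: 0.1398/(0.760 × 0.0667) − 2.387 = 0.372, power 64.5%.
- 22% less use, ratio 1/0.78 = 1.282, ln = 0.2485. Power 98.8% unadjusted, 99.4% adjusted.

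**Across the assumed range, 450 per arm.**

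| s | Difference | Unadjusted | b = 0.13 | b = 0.25 | b = 0.29 |
|---|---|---|---|---|---|
| 0.6 | 15% more | 86.6% | 88.3% | 92.7% | 94.6% |
| 0.8 | 15% more | 59.2% | 60.6% | 64.5% | 66.5% |
| 1.0 | 15% more | 38.6% | 39.3% | 41.2% | 42.2% |
| 0.8 | 22% less | 98.8% | 99.0% | 99.4% | 99.6% |
| 1.0 | 22% less | 91.0% | 91.5% | 92.8% | 93.4% |

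At s = 0.6 and 22% less, power is above 99.9% either way. The gain is 0.7 to 8.0 points for the 15% difference and at most 2.4 points for 22% less.

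**Sensitivity.** With 389 evaluable per arm, the central 15% case moves from 52.0% to 57.1%. In a wider grid at 389 per arm, with the SD of log platelets per m² at 0.6 and the SD of log BSA at 0.35, the 15% case moves from 66.3% to 80.6%; that is the extreme. For ratios of 1.5 or more the gain is negligible throughout. Any gain from the strata is not counted here.

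**The case against.** The strongest reply is that this is a choice between valid methods on a secondary endpoint. Randomisation protects the unadjusted test from bias, its type I error is correct, and the absolute total was chosen on purpose because cost follows platelets used. All of that stands. It does not answer the point, because on the log scale adding log BSA keeps the same target, the between-arm ratio of total platelets, and only narrows its standard error.

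The reply also notes that the size rests on assumed SDs and on the smaller of two background effects. That stands too. The 22% figure comes from an exact two-fold step, like adjacent arms here, and at that effect little is gained.

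Totals are only approximately proportional to BSA. The 25% dose tolerance, transfusions for bleeding or procedures, full doses for refractory patients and platelets in granulocyte products (sections 4.2, 5.2) all loosen the link and would reduce the gain.

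A reader might infer more than the protocol supports:
- *That the protocol ignores BSA.* It does not: outcomes 6 and 7 are scaled to BSA, and adjusted secondary analyses are planned. The gap is in the key test only.
- *That a chance imbalance of children biases the result.* Such imbalance is ordinary sampling variation, already in the standard error. With SD 0.25, the standard error of the arm difference in mean log BSA is 0.25 × 0.0667 = 0.017, about 1.7%.
- *That patients with no transfusion break the analysis.* Section 8.1 allows another transform or a Wilcoxon test, and both can accommodate zeros.
- *That cost calls for a log-link model of arithmetic means.* In simulation of the central 15% case, such a model with robust standard errors had power of about 45 to 48%, against about 58% for the planned t-test, a loss of about 10 to 13 points. The cost analysis (outcome 18) is separate and does not depend on this test.
- *That platelets per m² should be the tested outcome.* That moves away from the stated cost purpose.

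**Conclusion.** The point holds as a matter of efficiency. The key test of total platelets omits a baseline variable that determines each assigned dose, and some avoidable variance remains: about 10% in the central case, 2% to 23% over the assumed range (0.13²/1.0² to 0.29²/0.6²). The size depends wholly on assumed SDs and on the mix of adults and children, neither of which the protocol gives. It matters only if the true difference in use is near 15%. The validity of the test, the primary endpoint and the sample size are unaffected. Optional priority.

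**What to change.** In section 8.1, keep total platelets dispensed as the key secondary endpoint and keep the log (or other suitable) transform. Replace the two-sample t-test with a linear model for each pairwise comparison at the 0.017 level, with log BSA and the four randomisation strata as covariates. Report the unadjusted comparison as supportive, and leave the Wilcoxon fallback in place. With the log transform, present the result as an adjusted ratio of total platelets between arms; another transform would not give a ratio directly.

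The cost is a change of wording made before unblinded data are seen. Height and weight are already collected, and the model uses four degrees of freedom (one for log BSA, three for strata), which is trivial at this sample size. The drawback is that a model replaces a simple two-sample test.
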